#### **6.4.** WINDOWING CONVENTIONS

The following table describes assignment of visit windows for the purposes of analysis:

#### **Table A:** Visit Window

Assigned Study Day (Inclusive)		Visit Assigned	Week Assigned
From	То		
	-29	Visit 1	Week -4
-2	2	Visit 2	Week 0
53	59	Visit 3	Week 8

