#### **Protocol Template**

Sponsor: Menarini Pharmaceutical Study Code: MEIN/19/ZoNe-HYP/001

Protocol Version\_1 of 16/07/2020

ACE-i: Angiotensin converting enzyme-inhibitors; AE: Adverse event; BB: Beta blockers; ECG: electrocardiogram; EOT: End of treatment; NEB: nebivolol; SAE: serious adverse event; ZOF: zofenopril calcium

- a: For Visit 2, a window of ±2 days will be allowed at Week 0; and for Visit 3, a window of ±3 days will be allowed at Week 8
- b: Patients meeting the eligibility criteria at Screening, will enter the run-in period on the same day
- c: Patients on ZOF 30 mg or NEB 5 mg at Screening will continue the same therapy. Patients on any other ACE-i or BBs at Screening will be assigned to monotherapy with ZOF 30 mg or NEB 5 mg, respectively
- d: Patients will be provided with the extemporaneous combination of NEB 5 mg with ZOF 30 mg
- e: Adherence to monotherapies will be checked at the beginning of Visit 2
- f: Adherence to the extemporaneous combination of NEB 5 mg with ZOF 30 mg will be checked at the end of Visit 3
- g: To ensure patient safety, the patients will be contacted over phone within 24 hours, in case of any abnormality and clinically relevant laboratory test according to the Investigator's judgement at any visit
- h: Patients having any ongoing AE/SAE at the end of the treatment, will be followed for further 2 weeks via a phone call to check about the status of the AE/SAE

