### 2. Start of the assessment period (Visit 2, Week 0):

At the end of the run-in period (treatment with monotherapies for 4 weeks  $\pm 2$  days), only the patients with uncontrolled BP (SBP/DBP >130/80 mmHg), who tolerated the treatment and whose adherence to the therapy ranges from 80% to 120%, will enter the assessment period.

The starting of extemporaneous combination ZOF 30 mg /NEB 5mg dosing is noted as Week 0.

The following procedures/assessments must be completed:

- Recording of concurrent diseases and medical conditions
- Study drug dispensing (Patients will be provided with the extemporaneous combination ZOF 30 mg/NEB 5 mg)
- Recording of concomitant medications
- Physical examination and vital signs
- BP measurement
- ECG
- Urine pregnancy test (UPT)
- Compliance assessment by return of ZOF and NEB tablets (also empty blisters) and accountability
- AEs and serious adverse events (SAEs) assessment

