# 3. End of the Assessment Period (Visit 3, Week 8):

The end of assessment period will be considered as end of 8 week ±3 days treatment with the extemporaneous combination ZOF 30 mg/NEB 5mg.

Identification Number: FORM-000050125

Previous Doc Number:
CTWI10A

Version Number: 1.0, CURRENT

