### 6. GENERAL CONSIDERATIONS

### **6.1.** REFERENCE START DATE AND STUDY DAY

Study Day will be calculated from the reference start date and will be used to show start/stop day of assessments and events. Reference start date is defined as the day of the first dose of study drug (combination therapy) (Visit 2), (Day 1 is the day of the first dose of study drug ) and will appear in every listing where an assessment date or event date appears.

- If the date of the event is on or after the reference date, then:
- Study Day = (date of event reference date) + 1. If the date of the event is prior to the reference date, then: Study Day = (date of event – reference date).

In the situation where the event date is partial or missing, Study Day, and any corresponding durations will appear partial or missing in the listings.

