#### 7.3. MISSING DATA

Missing efficacy and safety data will not be imputed.

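### SAP Table A places the Week 8 window at Study Day 53-59, but the SAP's own Day 1 rule makes it Day 54-60, and the SAP does not say whether Table A or the nominal visit decides the primary Week 8 value

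*SAP*

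**What the plan says.** **Study Day.** SAP 6.1 takes the first combination dose, at Visit 2, as the reference date: "Day 1 is the day of the first dose of study drug". The formula then has two branches. "If the date of the event is on or after the reference date, then", one is added to the difference in dates. Before the reference date nothing is added. There is therefore no Day 0.

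**Visit 3.** The protocol ties the same dose to Week 0: "The starting of extemporaneous combination ZOF 30 mg /NEB 5mg dosing is noted as Week 0" (Protocol 7.1, Visit 2). Footnote a of the flow chart in Protocol 4.1, repeated in SAP 3.2, says "for Visit 3, a window of ±3 days will be allowed at Week 8". Protocol 7.1 describes Visit 3 as the "end of 8 week ±3 days treatment".

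**Analysis window.** SAP 6.4 introduces Table A as the assignment of visits for analysis. Its last row reads "53 59 Visit 3 Week 8".

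**Related rules.** SAP 6.3 says that by-visit summaries in general present data from the nominal visit. SAP 16.1.1 defines the primary variable as the DBP change from Week 0 (Visit 2) to Week 8 (Visit 3) and refers to neither rule. SAP 7.3 adds: "Missing efficacy and safety data will not be imputed". SAP 3.3 confines the primary analysis to observed data.

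**The concern.** The numbers 53 and 59 are elapsed days (56 ±3), whereas Table A is expressed in Study Days, which run one higher after the first dose. The row looks as though it was built without the added day.

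This row supplies the second half of every primary difference, and Visit 3 is the only scheduled visit after the start of combination treatment. If a program applies Table A literally, a patient seen on the last permitted day has no Week 8 value for DBP, SBP or BP goal, and nothing replaces it. A patient seen one day too early under the protocol is counted as on time.

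**Working it through.** **Inputs.** Day 1 = first combination dose at Visit 2; Study Day = elapsed days + 1 from that date on (SAP 6.1). Week 0 = start of combination dosing (Protocol 7.1). Visit 3 = 8 weeks = 56 days, ±3 (Protocol 4.1 and 7.1, SAP 3.2).

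**The plan's figures.** 56 − 3 = 53 and 56 + 3 = 59. Table A is reproduced exactly by elapsed days without the +1.

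**With the SAP 6.1 rule.** Lower limit (56 − 3) + 1 = 54; centre 56 + 1 = 57; upper limit (56 + 3) + 1 = 60.

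| Days after first dose | Study Day | Relative to 8 weeks | Protocol window | Table A |
|---|---|---|---|---|
| 52 | 53 | −4 | outside | Visit 3 |
| 53 | 54 | −3 | inside | Visit 3 |
| 56 | 57 | 0 | inside | Visit 3 |
| 58 | 59 | +2 | inside | Visit 3 |
| 59 | 60 | +3 | inside | none |
| 60 | 61 | +4 | outside | none |

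**Other rows of Table A.** The Visit 2 row runs from −2 to 2, which is symmetric about a Day 0 that does not exist. The Visit 1 row stops at −29. A run-in of 4 weeks ±2 days puts Visit 1 at 26 to 30 days before the dose, that is Day −26 to −30, so an on-schedule Visit 1 (Day −28) also falls in no window.

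**Readings at stake if Table A is applied.** The spread of visit days is not in the documents, so these shares on the +3 day are assumptions, for 216 readings all within ±3 days:

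- normal, SD 1.5 days: 3.9%, about 8 readings
- normal, SD 2 days: 7.1%, about 15
- uniform over the 7 days: 1/7 = 14.3%, about 31

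**Power of the test in the SAP.** SAP 16.1.3 tests no change, and SAP 6.5 makes tests two-sided at 5% by default. With the planned mean change of 4 mmHg and SD 10 mmHg, the noncentrality is (4/10)√n:

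- n = 216: 0.4 × √216 = 5.88, power 99.995%
- n = 185 (216 − 31): 0.4 × √185 = 5.44, power 99.97%

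**The case against.** **The row could be right on another calendar.** If the first combination dose were taken the day after Visit 2, then 8 weeks from Visit 2 would be Day 56 and 53-59 would fit; an on-schedule Visit 1 would be Day −29, matching that row's limit. This suggests one inconsistent origin behind several rows. But SAP 6.1 ties the reference date to Visit 2, Protocol 7.1 starts dosing at Week 0, and the footnote to Protocol Table 9.1 has visit-day tablets taken after that day's assessments. Alternatively, Week 8 might mean the 56th treatment day. Because visit-day doses follow the assessments, a Day 56 reading follows only 55 daily doses; the reading after 56 doses falls on Day 57. Neither reading agrees with the text.

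**Exclusion is not established.** A reader might infer that Day 60 readings necessarily drop out of the primary analysis. The documents do not support that. Under SAP 6.3 a scheduled Visit 3 reading keeps its nominal visit, SAP 16.1 does not invoke Table A, and the ITT definition has no window condition. On the other side, SAP 6.3 is limited to by-visit summaries and qualified as general, while Table A is stated to be for analysis. Precedence is open.

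**Power and bias.** A reader might also infer a real loss of power. On the sample-size basis (4 against a null of 2 mmHg, SD 10, one-sided 5%), power would fall from 90.1% at 216 to 85.7% at 185, but that is not the test specified in SAP 16.1.3. Nor do the documents link attending on day +3 with blood pressure, so bias from selective loss is unsupported. Accepting Day 53 would also partly offset lost readings: with an untruncated normal spread of SD 2 days, about 6.6% fall on +3 and 2.8% on −4. These objections stand and limit the consequence. They do not remove the offset.

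**Conclusion.** The Visit 3 row is wrong as written, by one day at each end. This follows from the SAP's Day 1 rule and the visit window that both documents state, and needs no outside assumption. One of the seven permitted days, Day 60, has no visit, and one impermissible day, Day 53, is admitted.

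The consequence is conditional. A compliant Day 60 reading may be excluded if Table A determines the Week 8 value; it stays in if the nominal visit does. The SAP leaves this undecided. The figures of 8 to 31 readings out of 216 rest wholly on assumed visit-day spreads and on Table A being applied. Even the largest leaves the power of the specified two-sided test practically unchanged under the planned effect and SD. The point concerns a clear, reproducible rule for the primary value; it does not show that the result is at risk.

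**What to change.** In a SAP revision before database lock:

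1. Change the Visit 3 row of Table A to Study Day 54 to 60.
2. Put the Visit 1 and Visit 2 rows on the same Day 1 origin, with no Day 0, so that all three rows match the protocol windows.
3. State in SAP 6.4 or 16.1 whether the nominal visit or Table A determines the Week 8 value in the primary analysis.

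The third item matters most, because the offset reaches the primary result only through that choice. The cost is a few lines of SAP text and the matching program change. No new data are needed, and the endpoint and test stay as they are, since the correction brings Table A into line with the protocol's own window.

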### **6.5.** STATISTICAL TESTS

The default significant level will be (5%); confidence intervals will be 95% and all tests will be two-sided, unless otherwise specified in the description of the analyses.

#### **6.6.** COMMON CALCULATIONS

For quantitative measurements, change from baseline will be calculated as:

• Test Value at Visit X – Baseline Value

And for change from Visit 1 will be calculated as:

• Test Value at Visit X – Visit 1 Value

#### **6.7. SOFTWARE VERSION**

All analyses will be conducted using SAS Enterprise Guide 7.1.

Document: \\ieedc-vnasc01\BIOSdata\Menarini\NebZof\KZA41200\Biostatistics\Documentation\SAP

Author: [name] Version Number: Final V1.0

Version Date: [14Dec2021]

Template No.: CS\_TP\_BS016 Revision 6 Reference: CS\_WI\_BS005

Effective Date: 02Dec2019

Page 20 of 37

#### 7. STATISTICAL CONSIDERATIONS

Summaries will include descriptive statistics for continuous variables (sample size [n], mean, standard deviation [SD], median, minimum and maximum) and for categorical variables (frequency [n] and percentage), unless otherwise stated in the relevant section. Percentages will be based on the number of patients within the relevant analysis population and treatment arm, or the number of patients with data available where relevant.

If the original data has N decimal places, then the summary statistics will have the following decimal places:

Minimum and maximum: N

Mean, median, Q1, Q3, confidence intervals, ratios: N + 1

SD: N+2

Percentages will be reported to one decimal place. P-values should be reported to three decimal places, except values <1.000 but >0.999 will be presented as '>0.999' (e.g., 0.9998 is presented as >0.999); and values <0.001 will be presented as '<0.001' (e.g., 0.0009 is presented as <0.001)

#### 7.1. ADJUSTMENTS FOR COVARIATES AND FACTORS TO BE **INCLUDED IN ANALYSES**

No adjustment for covariates will be performed for this study.

#### 7.2. **MULTICENTER STUDIES**

This study will be conducted by multiple investigators at multiple centers internationally. Center pooling will not be carried out for use in analyses for this study.

#### 7.3. MISSING DATA

Missing efficacy and safety data will not be imputed.

#### MULTIPLE COMPARISONS/ MULTIPLICITY 7.4.

Not Applicable

\\ieedc-vnasc01\BIOSdata\Menarini\NebZof\KZA41200\Biostatistics\Documentation\SAP Document:

Version Number: Final V1.0 Author: **[name]** 

> Version Date: [14Dec2021]

Reference: CS\_WI\_BS005 Template No.: CS\_TP\_BS016 Revision 6

Page 21 of 37

### 7.5. EXAMINATION OF SUBGROUPS

Subgroup analyses will be conducted as stated in the exploratory analysis sections. It should be noted that the study was not designed to detect treatment differences with high statistical power within subgroups.

The following subgroups will be assessed and described within the exploratory analysis sections on ITT and PP populations.

- Country/Site
- Age (<40 years and  $\ge40$  years)
- Gender (Male, Female, Other)
- Hypertension grade at screening (grade 1 and grade 2)
- Presence of diabetes (patients with or without diabetes)
- Presence of hypercholesterolemia (patients with or without hypercholesterolemia)
- Screening therapy (ACE-i, Beta blocker)
- Run-in period therapy (Monotherapies of ZOF 30 mg or NEB 5 mg)

Hypertension grade at screening is derived as follows;

- Grade  $1 140 \le SBP \le 160$  or  $90 \le DBP \le 100$
- Grade  $2 160 \le SBP \le 180$  or  $100 \le DBP \le 110$

Patients with presence of diabetes and hypercholesterolemia will be identified from the medical history data using the preferred terms. Presence of diabetes can be identified with the preferred terms "Diabetes mellitus" Or "Type 2 diabetes mellitus" and hypercholesterolemia with "Dyslipidaemia" or "Hypercholesterolaemia" or "Hyperlipidaemia". Patients under ACE-i and beta blocker can be identified from the concomitant medication data with anatomical therapeutic chemical (ATC) class "Ace inhibitors, plain" and "Beta blocking agents, selective" respectively.

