### Exploratory endpoint:

- Change in mean sitting SBP and DBP between Visit 1 and Visit 2:
   (a) in the group of patients who were on ZOF 30 mg and NEB 5 mg at Visit 1 and continued on the same treatment until Visit 2 and (b) in the group of patients, who switched to ZOF 30 mg or NEB 5 mg from any other ACE-i or BB at Visit 1 until Visit 2.
- Change in mean sitting SBP and DBP between Visit 1 and Visit 3: (a) in the group of patients who were on ZOF 30 mg and NEB 5 mg at Visit 1 and continued on the same treatment until Visit 2 and (b) in the group of patients who switched to ZOF 30 mg or NEB 5 mg from any other ACE-i or BB at Visit 1 until Visit 2.
- Number and proportion of patients achieving the BP goal (sitting BP ≤130/80 mmHg) at Visit 2 and Visit 3 evaluated in the patients: (a) who were on ZOF 30 mg and NEB 5 mg at Visit 1 or (b) who switched to ZOF 30mg or NEB 5 mg from any other ACE-i and BB at Visit 1
- Number and proportion of patients, divided in subgroups based on the hypertension grade, the presence or absence of diabetes, the presence or absence of hypercholesterolemia achieving the BP goal (sitting BP ≤130/80 mmHg) at Visit 2 and Visit 3

Study Population: Patients characteristics Number of Patients Approximately, 290 male or female Caucasian uncontrolled hypertensive patients between ≥18 and <65 years of age, who are on treatment with ZOF or NEB, or, on any other ACE-i or BBs, for at least 1 month, will be screened for eligibility.

A total drop-out rate of 25% from Visit 1 to Visit 3, has been considered. A

Identification Number: FORM-000050125

Previous Doc Number:
CTWI10A

Version Number: 1.0, CURRENT

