# 4.1 Study Flow Chart

Study Procedures/ Assessments	Visit 1 (Week -4)	Visit 2 (Week 0) a	Visit 3 (Week 8) a
	Screening +	Start of	End of
	Start of Run-in	Assessment	Assessment
	Period b	Period	Period
Informed consent	X		
Inclusion/exclusion criteria	Х		
Medical history	Х		
Prior medication	Х		
Demography (age, sex, race)	Х		
Concurrent diseases and medical conditions	Х	Х	Х
Antihypertensive treatment with NEB or ZOF monotherapy c	Х		
Study drug dispensing d		X	
Study drug return and accountability (Compliance assessment)		X e	X f
Concomitant medications	Х	Х	Х
Urine pregnancy test	Х	Х	Х
Physical examination	Х	Х	Х
Vital signs	Х	X	Х
Laboratory test 	X		Х
Blood pressure	X	X	Х
ECG	X	X	Х
AE/SAE assessment	Х	Х	X h

Identification Number: FORM-000050125

Previous Doc Number: CTWI10A

Version Number: 1.0, CURRENT

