#### 7. STUDY DESIGN

This is a phase IV, open-label, multicenter, multinational, interventional study to assess the effectiveness and safety of the extemporaneous combination of NEB and ZOF in grade 1 to 2 hypertensive patients versus each monotherapy (NEB or ZOF).

The study will be conducted in approximately 15 sites in the European Union countries. The total study duration is 12 weeks including a run-in period of 4 weeks and an assessment period of 8 weeks.

At Visit 1, after providing informed consent, the eligible grade 1-2 hypertensive patients (with blood pressure [BP] ranging from ≥140/90 mmHg to ≤179/109 mmHg), who were on treatment since at least 1 month, with any ACE-i or BB including ZOF 30 mg and NEB 5 mg will be screened for the eligibility criteria including BP. On the same day, the eligible patients will enter the run-in period of 4 weeks (Week -4 to Week 0). Efforts will be made to achieve 1:1 ratio in the enrolment of patients receiving any ACE-i or BB. The eligibility for grade 1-2 hypertension will be based upon the European Society of Cardiology/European Society of Hypertension (ESC/ESH) guidelines 2018, and the BP criteria is defined as mean sitting SBP ≥140 mmHg and ≤179 mmHg and/or mean sitting DBP ≥90 mmHg and ≤109 mmHg.

During the run-in period of 4 weeks (Week -4 to Week 0):

 Patients on ZOF 30 mg or NEB 5 mg will continue the same therapy. Patients on any other ACE-i will be assigned to monotherapy with ZOF 30 mg and the patients on any other BB will be assigned to monotherapy with NEB 5 mg, respectively.

Patients with controlled BP (sitting SBP/DBP ≤130/80 mmHg), at Week 0 (Visit 2), patients with uncontrolled BP (sitting SBP/DBP >130/80 mmHg) whose adherence to the treatment is not included from 80% to 120% or patients who cannot tolerate one of the monotherapies will not proceed further into the study.

Identification Number: FORM-000050125

Previous Doc Number:
CTWI10A

Version Number: 1.0, CURRENT

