### 11. MEDICAL HISTORY

Medical History information will be presented for the ENR.

- Medical History data captured on eCRF will be coded using Medical Dictionary for Regulatory Activities (MedDRA, Version 23.1 or latest) dictionary
  - Medical History conditions are defined as those conditions which stop prior to or at Screening.
  - Presented by SOC and PT.

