### 12. CONCURRENT DISEASES

Concurrent Diseases will be presented for the SAF by combination therapy.

- Concurrent Diseases will be coded using Medical Dictionary for Regulatory Activities (MedDRA, Version 23.1) dictionary
  - Concurrent Diseases are conditions started prior to or at Screening and are ongoing at the date of Screening.
  - Presented by SOC and PT.
  - Concurrent Diseases conditions are defined as those conditions recorded in the eCRF form "Concurrent Diseases and Medical Conditions".

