#### 16.3. EXPLORATORY EFFICACY

#### 16.3.1. EXPLORATORY EFFICACY VARIABLES & DERIVATIONS

- Change in mean sitting SBP and DBP between Visit 1 and Visit 2 in the group of patients on ZOF 30 mg and NEB 5 mg and in the group of patients switched to ZOF 30 mg or NEB 5 mg from any other ACE-I and BB
- Change in mean sitting SBP and DBP between Visit 1 and Visit 3 in the group of patients on ZOF 30 mg and NEB 5 mg or in the group of patients switched to ZOF 30 mg or NEB 5 mg from any other ACE-i and BB
- Number and proportion of patients in the group of patients on ZOF 30 and NEB 5 mg and in the group of patients switched to ZOF 30 mg or NEB 5 mg from any other ACE-I and BB achieving the BP goal (sitting BP ≤130/80 mmHg) at Visit 2 and Visit 3
- Number and proportion of patients on combination therapy, divided into subgroups specified under section 7.5, achieving the BP goal (sitting BP ≤130/80 mmHg) at Visit 2 and Visit 3

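### SAP 7.5 puts patients with discordant SBP and DBP in both hypertension grades, and does not say whether ongoing diabetes or hypercholesterolaemia counts as present

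*SAP*

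**What the plan says.** **Grade.** SAP 7.5 introduces the rule with "Hypertension grade at screening is derived as follows". Grade 1 is SBP 140 to 160 or DBP 90 to 100. Grade 2 is SBP 160 to 180 or DBP 100 to 110. All limits are inclusive in the text available. Nothing says which grade applies when the two pressures point to different grades. Protocol 7 sets entry as "mean sitting SBP ≥140 mmHg and ≤179 mmHg and/or mean sitting DBP ≥90 mmHg and ≤109 mmHg" and ties grade 1-2 eligibility to a named European guideline, but it states no rule for placing a patient in one grade.

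**Comorbidity.** SAP 7.5 states: "Patients with presence of diabetes and hypercholesterolemia will be identified from the medical history data using the preferred terms". SAP 11 says: "Medical History conditions are defined as those conditions which stop prior to or at Screening". SAP 12 says: "Concurrent Diseases are conditions started prior to or at Screening and are ongoing at the date of Screening", and it ties these conditions to their own eCRF form. The flow chart in Protocol 4.1 likewise gives "Concurrent diseases and medical conditions" a row separate from medical history.

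**Use.** The protocol's exploratory endpoints include a tally, with percentages, of those "divided in subgroups based on the hypertension grade, the presence or absence of diabetes, the presence or absence of hypercholesterolemia achieving the BP goal". SAP 16.3.1 takes this up for patients on combination therapy, "divided into subgroups specified under section 7.5, achieving the BP goal", and SAP 16.3.2 reports counts and percentages by subgroup.

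**The concern.** A two-level subgroup should place each patient once. With the two grades joined by 'or' on each side and no order of precedence, a discordant patient either appears in both rows of the table or lands in whichever grade the program tests first. Two programmers following SAP 7.5 faithfully could report Grade 2 groups of different size and make-up.

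The comorbidity rule raises a different problem. If the medical history data are what SAP 11 says they are, the 'with' groups hold only patients whose diabetes or hypercholesterolaemia had ended by Screening, and those with current disease sit in 'without'. The protocol's table of objectives and endpoints justifies these exploratory analyses by interest in patients with different cardiovascular risk factors, so that classification would defeat their purpose.

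What is at stake is the meaning and reproducibility of a named exploratory endpoint.

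**Working it through.** The plan gives no figure of its own to reproduce here. The check is a cross-reading of definitions plus a count of blood-pressure combinations.

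**1. Individual cases** (grade limits from SAP 7.5, entry limits from Protocol 7)

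| SBP/DBP | Strict upper limits | Limits as printed |
|---|---|---|
| 165/92 | both grades | both grades |
| 152/102 | both grades | both grades |
| 160/85 | Grade 2 only | both grades |

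The first two rows do not depend on whether a strict inequality sign was lost when the PDF was converted.

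**2. Count of integer pairs with SBP 140-179 and DBP 90-109** (40 × 20 = 800)

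- Strict limits: Grade 1 only, 20 × 10 = 200 (SBP 140-159, DBP 90-99). Grade 2 only, 20 × 10 = 200 (SBP 160-179, DBP 100-109). Both grades, 800 − 400 = 400.
- As printed: Grade 1 only, 20 × 10 = 200. Grade 2 only, 19 × 9 = 171 (SBP 161-179, DBP 101-109). Both grades, 800 − 371 = 429.

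So tightening the limits removes only 29 of the 429 overlapping pairs. The overlap comes from the 'or' without a priority rule. These are shares of grid cells, not of patients.

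**3. Illustration in patients.** The documents give no Screening BP distribution, so every input here is an assumption: bivariate normal values rounded to integers; SBP mean 148-156 with SD 10; DBP mean 90-94 with SD 7; correlation 0.2-0.6; restricted to inclusion criterion 3 with SBP no higher than 179 and DBP no higher than 109.

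- Share meeting both grades, strict limits: 0.137 (148/90, correlation 0.2) to 0.304 (156/94, correlation 0.2). As printed: 0.155 to 0.338.
- Central setting (152/92, correlation 0.4), strict limits: 0.212 meet both. Grade 2 holds 0.319 of eligible patients if it is tested first and 0.108 if Grade 1 is tested first.
- Wider inputs (SBP mean 145-160, SD 8-12; DBP mean 88-96, SD 6-8): 0.048 to 0.403.
- No simulated eligible patient falls in neither grade.

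**4. Comorbidity, sections side by side**

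| Condition at Screening | Category under SAP 11 and 12 | Source named in SAP 7.5? | Resulting subgroup |
|---|---|---|---|
| Stopped before or at Screening | Medical History | Yes | with |
| Ongoing | Concurrent Diseases | No | without |

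The documents give no prevalence for either condition, so the number misplaced cannot be computed.

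**The case against.** **The phrase may mean the wider record.** The same paragraph of SAP 7.5 identifies screening therapy from the concomitant medication data. SAP 13 defines concomitant drugs as those ending on or after the first dose of study medication, so a drug replaced at Visit 1 would not qualify. That rule works for switched patients only if the phrase means the record as collected, which under Protocol 9.5 includes drugs taken at enrolment. On the same footing, the medical history data could hold ongoing conditions. The eCRF and dataset specifications are not in the file. This stands: a reader might infer that the comorbidity groups will certainly be reversed, and the documents do not support that. What remains is that the only definitions given point that way and SAP 7.5 does not correct them.

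**The term list is not worded as exclusive.** SAP 7.5 says diabetes can be identified by two preferred terms, neither of them for type 1. This allows for others, and exclusion criterion 2 removes some patients with serious endocrine or metabolic disease. Both points hold, so the missing term carries little weight alone.

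**The overlap range is assumed.** It also describes patients eligible at Screening. SAP 7.5 runs the subgroups on ITT and PP, which require a dose of combination therapy, so those patients were still uncontrolled, tolerant and adherent at Visit 2. A reader might multiply the percentages by the planned 216. The documents do not support that, because the analysed set is selected on blood pressure.

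**A guideline rule may have been intended.** This is possible. The defect is that neither document states the rule, not that none was meant.

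**The outputs matter little.** They are descriptive, and SAP 7.5 itself warns of limited power in subgroups. SAP 3.3 notes that goal attainment at Visit 2 is zero by design, leaving one Visit 3 percentage per subgroup as the informative result. This sets the severity.

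**Conclusion.** The grade rule is wrong as written. Any patient whose SBP falls in one grade's range and DBP in the other's meets both, under strict or printed limits. That conclusion needs no assumption. How many patients this concerns is unknown. The figure of 14% to 30% of those eligible at Screening rests wholly on assumed distributions, and wider assumptions stretch it to about 5% to 40%.

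The comorbidity point is conditional: if SAP 7.5 is read with SAP 11 and 12, current disease is classed as absent. Its size cannot be stated.

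Severity is minor. The consequence is confined to the exploratory BP-goal tables by grade, diabetes and hypercholesterolaemia. A reader might infer that the efficacy conclusions are in doubt. They are not, since the pooled primary and secondary analyses do not use these groupings.

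**What to change.** In SAP 7.5:

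1. Define Grade 2 as SBP ≥160 or DBP ≥100 mmHg at Screening, and Grade 1 otherwise. On the grid above this puts 600 pairs in Grade 2, 200 in Grade 1 and none in both, so each eligible patient is assigned once. This is an analysis definition and leaves eligibility unchanged.
2. Identify diabetes and hypercholesterolaemia from Medical History plus Concurrent Diseases, and say whether a condition that ended before Screening counts as present.
3. Use a preferred-term list that has been reviewed before database lock. The data review meeting already planned in SAP 5 would serve.

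The cost is a few lines of SAP text and minor programming on data already collected. No patients, visits or tests are added.
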